- Individual subject success criteria defined as a 30% or greater reduction in self-reported Degree of Pain rating on the 0-100 VAS from baseline to study endpoint evaluation.

N.B.: The clinical relevance of a 30% change in VAS score is explained and supported in the STATISTICAL ANALYSIS PLAN section further along in this protocol document.

- Overall study success criteria of at least a 35% difference between the active device group and the placebo device group, comparing the proportion of individual successes in each group.
- It is anticipated that about 55% of subjects in the active device group and about 20% of subjects in the placebo device group will meet the individual success criteria, and
- intended application of a two-tailed test with an alpha value of 0.05 and Power of 0.8

...the sample size of 29 subjects per group (active group and placebo group, separately) has been determined using the following reference calculator: *Hypothesis Testing: Categorical Data - Estimation of Sample Size and Power for Comparing Two Binomial Proportions* in Bernard Rosner's *Fundamentals of Biostatistics*.

For the purposes of sample size calculation, it is anticipated that about one-twentieth of subjects overall may withdraw from the study prior to completion for various reasons. Therefore, the following formula is used to determine the final needed starting sample size for each group:

Final sample size = sample size X 1/(1-d); where d = # expected dropouts/# subjects enrolled.

Final sample size = 29 X 1/(1-0.083)

Final sample size = 29 X 1/0.917 = 29 X 1.0905 = 31.62, rounded to 32 subjects per treatment group.

Therefore, a minimum starting sample size of 32 subjects in each treatment group is needed to ensure that sufficient numbers remains at the end of the trial (29 subjects per group) for any significant differences found between groups to be considered statistically valid and representative of the general population being sampled. This results in a total of 64 subjects being enrolled in this study across both study treatment groups.

STUDY PROCEDURE

STUDY TEST BATTERY

The following are the study assessment tools to be used and the variables to be recorded in this clinical study.

BASELINE VARIABLES

A. Neuropathy Variables

- Number of months/years since onset of foot pain.
- Number of months/years since diabetes diagnosis
- Insulin dependency

B. Medication and Treatment

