- The treatment administration phase extends over 3 consecutive weeks.
- The subject self-administers two treatment administrations with the Erchonia® EVRL (A or B) on each consecutive day of the 3-week treatment administration phase for a total of 42 self-administered treatments.
- Each treatment administration lasts 5 minutes per foot, for a total of 10 minutes.
- Each treatment is self-administered by the subject in his or her own home.

TREATMENT ADMINISTRATION PHASE MEASURES

The following treatment administration phase measures will be recorded by the subject at home through the provided Case Report Forms (**Appendix M**).

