Records for each subject in this clinical study will be maintained in separate files in a locked filing cabinet at the respective test site. The investigator at the test site will be responsible for ensuring that all records for a subject pertaining to his or her participation in the clinical study are maintained in the subject's file at all times other than when information is being recorded on them.

Copies of all subject case report forms will be made and supplied to the study statistician and Erchonia Corporation who will each maintain these copies in a separate clinical study file that is kept in a locked filing cabinet on their respective premises. The original records will be maintained at the respective test sites.

Subjects' identities will be kept confidential by assigning each subject a unique de-identified subject ID upon acceptance into the study. The subject ID will comprise the investigator's two initials (first and last name initials) and a three-digit number that will be based upon the subject's order of entry into the clinical study. For example, under Study Investigator John Black, the third subject enrolled in the study would have a subject ID of JB003.

MONITORING OF THE CLINICAL STUDY

A Clinical Trial Monitoring Plan will be in place to ensure on-going compliance and accuracy of procedures throughout the trial.

STATISTICAL ANALYSIS

STUDY ANALYSIS POPULATIONS

(i) Intent-to-Treat (ITT) Population

The Intent-to-Treat (ITT) analysis population is defined as all consented and enrolled subjects. The ITT population will comprise the principal population analysis for evaluation of study primary efficacy outcome.

(ii) Per Protocol Population

The per protocol analysis population is defined as all consented and enrolled subjects who completed the entire clinical study per protocol, inclusive of all treatment administrations and all study activities and assessments per protocol without missing data or major protocol deviations. The per protocol population will comprise the secondary population analysis of the study primary efficacy outcome to provide support for the principal ITT population analysis as well as for all secondary outcome assessments.

HANDLING OF MISSING DATA

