Parametric Analysis of Covariance (ANCOVA) with the mean change from Baseline to study Endpoint (Week 3) in diabetic peripheral neuropathy foot pain ratings on the 0-100 VAS as the dependent variable, treatment group as the independent variable of interest, and Baseline diabetic peripheral foot pain VAS rating as a covariate will be performed. A two-tailed significance level of 5% was predetermined to be considered statistically significant.

SECONDARY EFFICACY OUTCOMES

The following secondary efficacy outcomes will be evaluated to provide support for the primary efficacy outcome analysis. **As no claims are intended to be made based on the secondary efficacy outcome evaluations, secondary efficacy outcome analysis will be performed for the per protocol analysis population only and statistical analyses will not be performed; secondary efficacy outcomes data will be presented descriptively only.**

(i) Diabetic Peripheral Neuropathy Foot Pain VAS Ratings Across Study Progression

Descriptives of mean, standard deviation (SD), median, and range (minimum, maximum) will be presented in a table for the degree of pain ratings recorded on the 0-100 VAS for diabetic peripheral neuropathy pain at each of the four (4) study assessments of Baseline (pre-treatment), Day 10 (Post-Baseline), Endpoint (3 Weeks Post-Baseline), and Follow-Up (7 Weeks Post-Baseline - 4 Weeks Post-Treatment End) by treatment group.

(ii) Neuropathic Pain Symptom Inventory (NPSI) Scores Across Study Progression

Descriptives of the mean, standard deviation (SD), median and range (minimum, maximum) for each of the five (5) dimension scores on the NPSI and the Total NPSI score will be presented in a table for each of the three study assessments of Baseline, Endpoint (Week 3), and Follow-Up (Week 7) by treatment group.

SATISFACTION WITH STUDY OUTCOME RATINGS

Subject satisfaction scores will be presented descriptively in a table as number (N) and percentage (%) per response category (Very Satisfied, Somewhat Satisfied, Neither Satisfied nor Dissatisfied, Not Very Satisfied, Not at All Satisfied) at each assessment of Study Endpoint (Week 3) and Study Follow-Up (Week 7) by treatment group.

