Ratings will be further categorized into 'positive satisfaction responses' by summing the 'very satisfied' and 'somewhat satisfied' categories. The proportion of 'positive satisfaction responses' in each category at each assessment visit between treatment groups will be compared using a chi-squared analysis with a two-tailed significance level of 5% considered statistically significant.

Additionally, Spearman's correlation analysis will be conducted to assess the relationship between subject satisfaction with treatment outcome ratings and mean change in subject VAS ratings for diabetic peripheral neuropathy foot pain from Baseline to study Endpoint (Week 3), and from Baseline to Follow-Up (Week 7) assessments.

CHANGES IN MEDICATION USE AND TREATMENT COMPLIANCE

Subject compliance with treatment administration and maintenance of medication use reported at baseline without change across study duration will be assessed and reported descriptively based on subject recordings on the Subject Daily Diary.

BLINDING EFFICACY EVALUATION

Blinding efficacy evaluation will be conducted through analysis of findings from the Subject Perceived Subject Group Allocation and Rationale responses, recorded at completion of the treatment administration phase (study endpoint).

Statistical evaluation of blinding efficacy will be performed as follows:

- (i) The number (N) and percentage (%) of subjects who correctly perceived their treatment group assignment and the percentage of subjects who did not correctly perceive their treatment group assignment will be calculated for each treatment group.
- (ii) A Chi-Squared Analysis to assess the significance of the difference in the proportion of subjects who accurately perceived their Baseline treatment group assignment between the active and placebo treatment groups at each of Endpoint (Week 3) and Follow-Up (Week 7) assessments will be performed. A two-tailed significance level of 5% will be considered statistically significant.

- (i) **Qualitative analysis confirmation:** Evaluation of the comments provided by the subject in the rationale section to explain the guess at group assignment will be evaluated and interpreted as follows to either support or negate the numerical findings:

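### Secondary outcomes are shown only for subjects with all 42 sessions and every assessment to Week 7, so they never describe the randomised groups; whether satisfaction falls under that rule is unclear

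*Combined protocol and SAP*

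**What the plan says.** Under Study Analysis Populations, ITT is the principal population for the primary outcome. The per-protocol population supports that analysis and also serves all secondary outcome assessments. It consists of subjects who completed the whole study, "inclusive of all treatment administrations and all study activities and assessments per protocol without missing data or major protocol deviations". The word *major* qualifies deviations only. The requirements for every treatment and for no missing data carry no tolerance.

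The Treatment Administration Protocol prescribes two sessions a day for three weeks, "for a total of 42 self-administered treatments". The last assessment is the 7 Week Evaluation, four weeks after treatment ends.

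Under Secondary Efficacy Outcomes, the SAP says that "secondary efficacy outcome analysis will be performed for the per protocol analysis population only and statistical analyses will not be performed". The reason given is that no claims will rest on these outcomes, but the same paragraph says they are evaluated to support the primary. Two outcomes are then numbered: the VAS course and the NPSI.

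Satisfaction appears beside the NPSI under Secondary Outcome Measures in the protocol part. In the SAP it has its own heading after the numbered list. There, the proportions with a positive response at Weeks 3 and 7 "will be compared using a chi-squared analysis with a two-tailed significance level of 5% considered statistically significant", and Spearman correlations with VAS change are added.

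**The concern.** Completing every session and every form happens after randomisation, in an unsupervised home regimen, and may depend on how the subject is doing. A comparison restricted to such subjects no longer has the balance that randomisation provides. It also discards usable data: a subject with a valid Week 3 VAS and NPSI disappears from the Week 3 tables because of one missed session, or because of a form due four weeks later.

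The stake is the supporting evidence. Readers of the NPSI and follow-up VAS tables would take them as describing the trial's two arms, when they describe full completers of unknown number. The per-protocol repeat of the primary has the same weakness and may be small. For satisfaction, an analyst cannot tell from the text which population to use or whether the no-testing rule applies.

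**Working it through.** **1. The plan's own figure.** Inputs from Rationale for sample size: "two-tailed test with an alpha value of 0.05 and Power of 0.8", and "about 55% of subjects in the active device group and about 20% of subjects in the placebo device group". With pooled proportion (0.55 + 0.20)/2 = 0.375,

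n = [1.96·√(2·0.375·0.625) + 0.8416·√(0.55·0.45 + 0.20·0.80)]² / 0.35² = 28.8, rounded up to 29.

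This reproduces "the sample size of 29 subjects per group". Enrolment is 29/0.917 = 31.62, rounded up to 32 per arm (64 in all). The text says "it is anticipated that about one-twentieth of subjects overall may withdraw", which would give 29/0.95 = 30.53, so 31; that mismatch is a separate matter. What matters here is that the allowance covers withdrawal. A missed session is not a withdrawal, and the plan has no allowance for it.

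**2. Which population each outcome gets.**

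| Outcome | ITT | Per protocol |
|---|---|---|
| Week 3 VAS responders | yes, principal | yes, supportive |
| Day 10 and Week 7 VAS | no | yes |
| NPSI, all visits | no | yes |
| Satisfaction, Weeks 3 and 7 | none stated | yes, by the population definition |

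**3. Size of the per-protocol set.** The documents give no session adherence, so p below is an assumption. If single sessions are missed independently, the share with all 42 is p^42. If misses are whole days, it is p^21.

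| p | p^42 | of 64 | p^21 | of 64 |
|---|---|---|---|---|
| 99% | 66% | 42 | 81% | 52 |
| 98% | 43% | 27 | 65% | 42 |
| 97% | 28% | 18 | 53% | 34 |

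Half the sample is lost at p = 0.5^(1/42) = 98.4% with independent misses, or 0.5^(1/21) = 96.8% with whole-day misses. If misses cluster within subjects (beta-binomial, intraclass correlation 0.05 to 0.30), mean adherence of 98% leaves 64–86% and 95% leaves 32–69%. Withdrawals and missing forms come on top of all these figures.

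**4. The per-protocol repeat of the primary.** Exact power of the uncorrected chi-squared test at 55% v 20% is 85.2% with 32 per arm, 79.6% with the planned evaluable 29, 67.6% with 21, and 48.4% with 14. The last two sizes are 32 × 0.656 = 21.0 and 32 × 0.428 = 13.7. Whole-day misses at 98% also give about 21 (32 × 0.654 = 20.9). These figures do not apply to the VAS course or NPSI, which are not tested.

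**5. Satisfaction.** If the class given under Secondary Outcome Measures governs, the no-testing rule and the chi-squared test conflict. If the rule covers only the two outcomes numbered beneath it, both can be followed, but the per-protocol-only sentence then no longer reaches satisfaction. The population definition, which covers all secondary outcomes, still would. The text does not choose between these readings.

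**The case against.** The restriction is prespecified and no claims are intended from the secondary outcomes. The primary is decided in ITT, individual Baseline and Week 3 VAS ratings are listed, and site-level primary data use ITT. All of this stands and limits the seriousness of the point. It does not supply an ITT view of the NPSI, the Day 10 and Week 7 VAS, or satisfaction.

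Three stronger readings are tempting, and the documents do not support them.

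- *The secondary sample will be halved.* That needs an adherence rate and a pattern of misses that the plan does not give, and clustering softens the loss. The compliance log asks for a daily record, so a single missed session may not even be captured.
- *The selection will inflate the treatment effect.* No document says how completion relates to benefit. An illustration with invented completion rates, 55% in responders and 30% in non-responders in both arms, turns 55% v 20% into 0.3025/0.4375 = 69% v 0.11/0.35 = 31%. Both arms rise, but the difference moves only from 35 to 38 points. Comparability is lost; the direction and size of any bias are unknown.
- *The plan contradicts itself on testing the secondary outcomes.* The VAS course and NPSI are descriptive throughout. The question concerns satisfaction alone, and its separate SAP heading permits a consistent reading.

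It is also fair to object that ITT tables filled by the rule under Handling of Missing Data would not be an improvement. Replacing missing values with a group mean or median shrinks the standard deviations being tabulated. In addition, ITT means consented and enrolled subjects while randomisation precedes qualification, so who contributes data must be shown.

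**Conclusion.** The point holds in limited form. As written, the NPSI, the Day 10 and Week 7 VAS and, by the population definition, satisfaction are presented only for a set chosen by complete post-randomisation behaviour through Week 7. The same set provides the supportive Week 3 primary analysis. That follows from the text and needs no assumption.

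The size of the loss is unknown. At 98–99% session adherence it could leave roughly 43–66% of subjects with independent misses, or 65–81% with whole-day misses; both the rates and the patterns are assumptions. The principal ITT analysis of the Week 3 primary is not affected. Satisfaction's status is an ambiguity to resolve, not a proven contradiction. The change is worth making because the data are already collected and the present tables cannot do the supporting job the plan gives them.

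**What to change.** 1. **Secondary Efficacy Outcomes.** Present every secondary outcome, including satisfaction, by randomised group in the ITT set as observed cases, with the number contributing at each visit. Do not apply the group mean or median imputation to these tables. Keep the per-protocol tables as support.
2. **Per Protocol Population.** For Week 3 analyses, define the set on data through Week 3 only. Replace the all-sessions requirement with a minimum number of completed sessions, fixed and justified by the sponsor before unblinding. The documents give no basis for a particular number. This is a rule for the analysis set and leaves the prescribed treatment unchanged.
3. **Satisfaction.** State whether it is a secondary efficacy outcome and which population it uses. Reconcile the two SAP sections by reporting the between-arm difference in positive responses with a 95% confidence interval, and the Spearman correlations, all labelled descriptive.

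The cost is SAP wording and one more set of tables from data already being collected. The ITT secondary results may look less favourable than the per-protocol ones.

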PMID: 15030944

The full article and the NPSI Assessment tool are contained in **Appendix K** of this clinical study protocol.

Subject Satisfaction With Study Outcome

The subject is asked to rate how satisfied he or she is with any change in his or her overall foot pain following completion of the laser administration procedures with the Erchonia® EVRL by using the 5-point Likert scale presented below to respond to the following question: "Overall, how satisfied or dissatisfied are you with any change in your foot pain following the study procedures with the study laser device?"

- Very Satisfied
- Somewhat Satisfied
- Neither Satisfied nor Dissatisfied
- Not Very Satisfied
- Not at All Satisfied

BLINDING EFFICACY EVALUATION TOOLS

Subject Perceived Group Allocation and Rationale

The subject records whether he or she believes to have received the study treatments with the true or fake Erchonia® EVRL and records verbatim his or her reasoning or rationale for this perceived determination.

STUDY PROCEDURE PROTOCOL

STUDY QUALIFICATION

SIGNING OF INFORMED CONSENT FORM

The investigator will commence by presenting and reviewing in detail the items in the informed consent form with the individual and answer any questions. To proceed, the individual must willingly sign the informed consent form.

ASSIGNMENT OF SUBJECT IDENTIFICATION NUMBER

The subject is assigned to a unique subject identification number based upon his or her order of entry into the study.

Additional information about the informed consent and subject ID number assignment is contained in a later section of the protocol titled, "SAFETY AND CONFIDENTIALITY ISSUES."

SUBJECT RANDOMIZATION TO TREATMENT GROUP

Following signing of the consent form and prior to study qualification evaluation, a subject is randomly assigned to Treatment Group A or to Treatment Group B, following the methodology outlined above in the STUDY DESIGN section of the protocol.

STUDY QUALIFICATION CHECKLIST

To be eligible for study participation, a subject must satisfy the following qualification criteria:

INCLUSION CRITERIA

To be eligible for study participation, a subject must satisfy each of the following criteria.

- Previously diagnosed with diabetes induced peripheral neuropathy by a suitably qualified and licensed health professional within the past 6 months.

- Over the age of 18 years.
- Able to read and write English.
- Constant feet pain on-going over at least the past 3 months.

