 - *Positive blinding efficacy* will be supported through qualitative assessment of comments provided to support perceived group assignment that pertain to the determination being based on treatment efficacy or lack thereof, e.g.: 'My foot pain is much less than it used to be, so I believe I got the real treatment' or 'My foot pain hasn't really changed, so I believe I got the fake treatment.'
 - *Blinding will be determined to have failed* if comments provided to support perceived group assignment pertain to factors such as sensation/visual clues or overhearing conversations by research staff members.

INDIVIDUAL SUBJECT VAS RATINGS ACROSS STUDY DURATION

Individual subject data for the Primary Outcome Measure of diabetic peripheral neuropathy foot pain VAS Ratings as recorded at each of Baseline (pre-treatment) and Study Endpoint (Week 3) assessments, by Treatment Group, by Test Site, will be presented in table format.

INDIVIDUAL TEST SITE DATA

Key demographic and neuropathy variables and the primary outcome assessment for the ITT analysis population will be presented by treatment group by each of the four individual test sites participating in this study. Data will be presented in descriptive format only due to the small sample sizes that preclude statistical conclusions from being validly drawn.

SAFETY ANALYSES

Safety analyses will be based on all subjects who were randomized to the test or to the placebo treatment group. Safety will be assessed by evaluating and comparing frequency and incidence of observed and/or reported adverse events between test and placebo treatment groups. A chi-square test with a continuity correction will be performed to compare the percentage of subjects who had adverse events between test and placebo treatment group subjects.

INFORMED CONSENT

- Informed consent will be an agreement between the individual investigator and each subject, having the capacity to understand and make an informed decision. Consent will be obtained prior to each potential subject's participation in this clinical study.

- Each subject participating in this clinical study will be made aware of the fact that his or her participation involves research and the intent of the research, the expected duration of his or her participation and a description of the procedures that will be followed.
- Each subject will be made aware of the reasonably expected benefits he or she might receive, as well as any risks or potential discomfort that are involved.

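### The planned blinding test compares the share of correct guesses between arms, which does not test whether guess and assignment are associated

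*Combined protocol and SAP*

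**What the plan says.** Under Blinding Efficacy Evaluation Tools the guess has two answers: "The subject records whether he or she believes to have received the study treatments with the true or fake" device. It is recorded after treatment, at the 3-week and 7-week evaluations.

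The Blinding Efficacy Evaluation section of the Statistical Analysis then has three parts:

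- Item (i) is descriptive. It reports, for each arm, the count and share "of subjects who correctly perceived their treatment group assignment and the percentage of subjects who did not correctly perceive their treatment group assignment".
- Item (ii) is the only significance test: "A Chi-Squared Analysis to assess the significance of the difference in the proportion of subjects who accurately perceived their Baseline treatment group assignment". It compares the two arms at Week 3 and again at Week 7, two-tailed at 5%.
- A qualitative review of the subjects' stated reasons is to be "interpreted as follows to either support or negate the numerical findings". Comments that "pertain to the determination being based on treatment efficacy or lack thereof" count as blinding upheld. The failure rule applies "if comments provided to support perceived group assignment pertain to factors such as sensation/visual clues or overhearing conversations by research staff members".

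The Rationale for Sample Size gives the planned rates of individual success: "It is anticipated that about 55% of subjects in the active device group and about 20% of subjects in the placebo device group". It sets 29 completers and 32 enrolled per group.

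**The concern.** A blinding check usually asks whether guess and actual assignment are associated. Item (ii) asks whether the two arms are equally accurate. The two questions can have opposite answers. If most subjects in both arms say 'true', accuracy is high in the active arm and low in the placebo arm although the guess carries no information about assignment. If most subjects in both arms identify their device, accuracy is equal and the test has nothing to detect.

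The primary outcome is a self-reported pain score recorded at home, so readers will look to the blinding evaluation when they interpret it. A false alarm and a false reassurance are both possible.

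**Working it through.** **Inputs.** Binary guess (Blinding Efficacy Evaluation Tools); two-tailed 5% chi-squared test (Blinding Efficacy Evaluation, item (ii)); 32 enrolled and 29 completing per arm, and response of 55% versus 20% (Rationale for Sample Size). The documents give no guess rates, so those below are assumptions. They also give no error rate or power for the blinding test, so the only figures of theirs to reproduce are the arm sizes:

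- n = [1.960·√(2·0.375·0.625) + 0.842·√(0.55·0.45 + 0.20·0.80)]² / 0.35² = 28.8, so 29
- 29 / (1 − 0.083) = 31.62, so 32

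Both agree with the plan.

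**The hypothesis tested.** Let a and b be the shares guessing 'true' in the active and placebo arms.

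- Share correct: a in the active arm, 1 − b in the placebo arm.
- Null of item (ii): a = 1 − b, that is a + b = 1.
- Null of no association between guess and arm: a = b.

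The two coincide only at a = b = 0.5. If a = b = q, item (ii) is in effect a test of q = 0.5. If both arms are correct with probability c, then a = c and b = 1 − c, and the null of item (ii) is true whatever the value of c.

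**Two worked tables, 32 per arm.** With x and y the counts compared and t = x + y, χ² = 64(x − y)² / [t(64 − t)].

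- 24/32 guess 'true' in each arm, so 24/32 versus 8/32 are correct. Planned test: 64·16²/(32·32) = 16.0, p = 0.00006. Guess-by-arm test: 24 versus 24, χ² = 0.
- 29/32 correct in each arm, so 29/32 versus 3/32 guess 'true'. Planned test: χ² = 0. Guess-by-arm test: 64·26²/(32·32) = 42.25, p = 8 × 10⁻¹¹.

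**Probability of a significant result.** Exact enumeration of two binomials, uncorrected chi-squared, critical value 3.84; tables with an empty margin count as not significant. The planned test compares a with 1 − b, the guess-by-arm test a with b. Entries are for 32 per arm, with 29 per arm in brackets.

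| Assumed guesses | a, b | Planned test | Guess-by-arm test |
|---|---|---|---|
| Unrelated to arm | 0.50, 0.50 | 0.06 (0.05) | 0.06 (0.05) |
| | 0.55, 0.55 | 0.14 (0.12) | 0.06 (0.05) |
| | 0.60, 0.60 | 0.39 (0.33) | 0.06 (0.05) |
| | 0.65, 0.65 | 0.71 (0.63) | 0.05 (0.05) |
| | 0.70, 0.70 | 0.92 (0.88) | 0.05 (0.05) |
| | 0.75, 0.75 | 0.99 (0.98) | 0.05 (0.05) |
| Equally unblinded, 70% correct | 0.70, 0.30 | 0.05 (0.05) | 0.92 (0.88) |
| 80% correct | 0.80, 0.20 | 0.05 (0.05) | 1.00 (1.00) |
| 90% correct | 0.90, 0.10 | 0.06 (0.05) | 1.00 (1.00) |
| Unequally unblinded, 90% vs 70% correct | 0.90, 0.30 | 0.53 (0.48) | 1.00 (1.00) |
| 90% vs 50% correct | 0.90, 0.50 | 0.96 (0.94) | 0.96 (0.94) |
| Guess equals response | 0.55, 0.20 | 0.59 (0.53) | 0.85 (0.80) |
| Partly follows response, 90% / 50% | 0.72, 0.58 | 0.71 (0.64) | 0.22 (0.19) |
| Partly follows response, 90% / 30% | 0.63, 0.42 | 0.08 (0.06) | 0.42 (0.36) |

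In the last two rows r and s are the shares of responders and non-responders saying 'true', with a = 0.55r + 0.45s and b = 0.20r + 0.80s. For r = 0.9, s = 0.5: a = 0.495 + 0.225 = 0.72 and b = 0.18 + 0.40 = 0.58. For r = 0.9, s = 0.3: a = 0.495 + 0.135 = 0.63 and b = 0.18 + 0.24 = 0.42.

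When guesses are unrelated to arm, the planned test passes probability 0.5 at about 62% guessing 'true' (63% at 29 per arm). A majority guessing 'fake' has the same effect by symmetry.

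**Continuity correction.** Item (ii) does not mention one. With Yates' correction the planned test gives 0.62 (0.53) at 65% guessing 'true' and 0.88 (0.81) at 70%. When both arms are equally unblinded at 70% to 90% correct it gives 0.03 or less.

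**The case against.** No decision rests on this p-value. Item (ii) does not say that significance means failure or that non-significance means success; the only explicit failure rule is the comment review. Item (i) already reports correct and incorrect guesses by arm, which for a binary guess is the full guess-by-arm table, so a reader could see either worked pattern and compute the association. By the plan's own criterion the replacement is not always better: efficacy-based guesses count as blinding upheld, and in two of the three efficacy-driven rows the guess-by-arm test is significant more often than the planned one. All guess rates are assumed, and the case report form is not available, so a 'don't know' option cannot be ruled out.

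Much of this stands. It limits the consequence to what the trial can say about blinding, and it means the new test cannot be a verdict on its own. It does not rescue item (ii). The section presents that test as part of its statistical evaluation of blinding, and the comments are meant to support or negate numerical findings that, as tested, are not about association. No test or rule is attached to the percentages in item (i). Neither test is always the quieter one when guesses follow efficacy, but the guess-by-arm result has a clear meaning that the comments can then explain. The planned p-value mixes that association with a general tendency to say 'true'. A 'don't know' answer would change the exact null and the probabilities, but a comparison of accuracy would still not test association.

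**Conclusion.** The concern holds. With a true/fake guess, item (ii) tests a + b = 1, not a = b. It is likely to be significant when guesses are unrelated to arm but about 65% or more say 'true' (0.71 at 32 per arm and 0.63 at 29, rising to 0.92 and 0.88 at 70%). It is significant only about 5% of the time when both arms are equally unblinded, where a guess-by-arm test has probability 0.88 or more.

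The algebra depends only on the binary guess. The probabilities depend on assumed guess rates and the uncorrected test; Yates' correction lowers them without changing the direction. Intact blinding implies a = b only if guesses do not follow felt benefit, so a guess-by-arm test does not by itself show whether blinding held. The primary success decision and all claims are unaffected. This should be corrected, because the test as written can mislead about blinding in either direction.

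**What to change.** In Blinding Efficacy Evaluation, replace the test in item (ii) with a cross-tabulation of guess (true or fake) by actual group. Apply a chi-squared or Fisher test to the proportion guessing 'true', at Week 3 and at Week 7. A per-arm blinding index with a 95% confidence interval is optional. Keep the percentages in item (i) and the review of comments.

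State in the SAP that the new test measures association between guess and arm, that a significant result alone is not a blinding failure, and that it must be read with the comments.

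The cost is SAP wording and one different 2×2 table at each of two visits, from the same data. The downside is sensitivity to efficacy-driven guesses: if guesses followed the planned response exactly, the new chi-squared test would be significant with probability 0.85 (0.80 at 29 per arm), against 0.59 (0.53) for the planned test. Fisher's test would give 0.78 (0.71) there, about 0.03 (0.02 to 0.03) when guesses are unrelated to arm, and 0.88 (0.81) when both arms are 70% correct.
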